1. OBJECTIVES

The objective of this study is to determine whether combination therapy with tivozanib and enzalutamide is an effective and well tolerated regimen in men with advanced prostate cancer.

1.1 Study Design

We plan to conduct a single arm, open label, combination study with tivozanib and enzalutamide (enz) in men with metastatic castration resistant prostate cancer (mCRPC). All men will receive standard dosing of each drug, with tivozanib administered at 1.5 mg once daily for 3 weeks followed by a one-week break, and enzalutamide taken continuously at 160 mg once daily. Both will be orally administered. A single dose reduction of tivozanib will be permitted, if necessary, to 1.0 mg daily. Patients will continue on treatment until they experience objective or clinical disease progression, or unacceptable toxicity.

Because this combination has not been previously tested, a safety run-in will be conducted at the outset of the trial. While waiting for the first 3 patients to complete one month of treatment, no more than 10 total patients may be enrolled. These patients will be analyzed for safety and toxicity. If any treatment-related, expected or unexpected grade 3 or higher adverse events occur during the first month of treatment in the first 3 patients, or if the rate is >30% among the first 10 patients during the first month of treatment, further accrual will be halted for reconsideration of the appropriateness of the dosing schedules.

1.2 Primary Objectives

The primary objective of the study will be to demonstrate an improvement in progression free survival in men with mCRPC treated with tivozanib and enzalutamide.

1.3 Secondary Objectives

Secondary objectives will be to demonstrate an acceptable tolerability profile of tivozanib and enz, to estimate overall survival and time to PSA progression, to evaluate PSA and objective response and to explore an angiogenesis signature that may predict benefit from VEGFR-targeted therapy in advanced prostate cancer.

2. BACKGROUND

2.1 Study Agent(s)

2.1.1 Tivozanib

2.1.1.1 Tivozanib Background

Tivozanib hydrochloride (also known as AV-951; previously known as KRN951) has the chemical name (*N*-{2-Chloro-4-[(6,7-dimethoxy-4-quinolyl)oxy]phenyl}-N'-(5-methyl-3-isoxazolyl)urea hydrochloride monohydrate). Tivozanib hydrochloride is a novel and potent pan-vascular endothelial growth factor (VEGF) receptor tyrosine kinase inhibitor with potent CONFIDENTIAL

activity against all 3 VEGF receptors (VEGFR-1, -2, and -3). Tivozanib hydrochloride inhibits phosphorylation of VEGF receptors-1, -2 and -3 at picomolar concentrations (IC $_{50}$ of 0.21, 0.16 and 0.24 nM respectively), and inhibits c-Kit and PDGFR at 10-times higher concentrations (IC $_{50}$ of 1.63 and 1.72 nM respectively). In nonclinical models and studies performed in humans, tivozanib hydrochloride has shown strong anti-angiogenesis and antitumor activity. VEGF is a potent induction factor, playing a central role in angiogenesis and vascular permeability of tumor tissues. By inhibiting VEGF-induced VEGFR activation, tivozanib hydrochloride inhibits angiogenesis and vascular permeability in tumor tissues, leading indirectly to inhibition of tumor growth.

Tivozanib hydrochloride has been studied in several clinical trials in multiple tumor types. A summary of tivozanib's hydrochloride pertinent efficacy results and safety data follow. Please refer to the tivozanib hydrochloride Investigator Brochure (IB) for descriptions of all available data.

2.1.1.2 Tivozanib Clinical Experience

In phase 1 clinical trials of tivo, different doses and schedules were studied, and PK properties were further defined. Based on these studies, the preferred dosing regimen for additional studies was identified as 3 weeks of once-daily dosing followed by a one-week break, at a starting dose of 1.5 mg daily.

In a Phase 2 study (AV-951-07-201) in 272 patients with metastatic renal cell carcinoma (RCC), there were 2 primary efficacy analyses: best tumor response rates throughout the 16-week open-label period and progression-free survival (PFS) rates at 12 weeks post-randomization. Throughout the 16-week, open-label period, the overall response rate (ORR) for all treated subjects was 24.6% by investigator assessment and 18% by independent radiology review (IRR) assessment. By both investigator assessment and IRR assessment, the disease control rate (DCR) for all treated subjects was 84.2% (229/272 subjects). At 12 weeks post-randomization, PFS rates were 57.4% for tivozanib hydrochloride subjects and 28.1% for placebo subjects (p=0.001). By IRR assessment, PFS rates were 49.2% for tivozanib hydrochloride subjects and 21.1% for placebo subjects (p=0.001)¹.

This promising clinical activity in patients with renal cell carcinoma ultimately led to a registrational, international phase 3 trial of tivozanib in metastatic RCC. The phase 3 trial of randomized patients in 1:1 fashion to treatment with either tivozanib or sorafenib, another small molecule receptor tyrosine kinase inhibitor previously approved for the treatment of mRCC². The primary endpoint was PFS, and tivozanib significantly prolonged PFS compared with sorafenib, 11.9 versus 9.1 months, respectively³. The adverse event profile of tivozanib was favorable as well, with primarily on-target and easily managed adverse events such as hypertension. Tivozanib has not previously been studies in men with prostate cancer.

2.1.1.3 Tivozanib Safety Experience

Excluding the phase 3 trial, safety data are summarized below for 14 completed or ongoing clinical studies of tivozanib. Adverse events were generally manageable using standard medical therapy and/or discontinuation or reduction of study drug.

Related treatment emergent adverse events (TEAEs) that resulted in a fatal outcome occurred in 4 subjects and included post-procedural hemorrhage, cerebrovascular accident, pulmonary embolism, and hypertension.

Related TEAEs for combination therapy studies can be summarized as follows:

Combination therapy studies: Related TEAEs were reported in 65/81 subjects (80.2%). The most frequently related TEAEs (occurring in \geq 10% of treated subjects) were fatique (50.6%), nausea (40.7%), diarrhea (35.8%), stomatitis (33.3%), vomiting (24.7%), decreased appetite (23.5%), hypertension (22.2%), peripheral sensor neuropathy (22.2%), epistaxis (19.8%), dysphonia (16.0%), thrombocytopenia (16.0%), alopecia (14.8%), headache (12.3%), neutropenia (12.3%), and blood triglycerides increased (11.1%).

RCC monotherapy studies: Treatment-emergent adverse events occurring in $\geq 10\%$ of the total number of subjects in the 4 core RCC monotherapy studies (Studies AV 951-09-301, AV-951-07-201, AV-951-10-202, and AV-951-09-902) treated with tivozanib hydrochloride are presented by preferred term for subjects in the 4 core RCC monotherapy studies in the table below. The table also presents TEAEs for subjects treated with tivozanib hydrochloride in the Phase 3 Study AV 951-09-301/902. TEAEs were reported in 681 of the 785 subjects treated with tivozanib hydrochloride (86.8%). The most frequently reported TEAEs in tivozanib hydrochloride-treated subjects were hypertension, dysphonia, fatigue, and diarrhea. Hypertension, the most frequently occurring TEAE, is a recognized side effect of VEGF receptor inhibitors, the class of drug to which tivozanib hydrochloride belongs, and is likely related to the mechanism of action of these drugs. Across the 4 core RCC monotherapy studies, the incidence of hypertension was lowest in subjects in Study AV-951-09-902 (35 subjects, 23.5%), when tivozanib hydrochloride was given as a next-line VEGF receptor inhibitor after progression on sorafenib in Study AV-951-09-301. In subjects treated as randomized in Studies AV-951-07-301/902 (ie, subjects randomized in Study AV-951-07-301 and continuing with their randomized treatment after rollover into Study AV-951-09-902), the overall incidence of AEs reported in the tivozanib hydrochloride group was 90.7% (235 subjects). The AE profile was similar between tivozanib hydrochloride and sorafenib-treated subjects, although the incidence of on-target toxicities (hypertension and dysphonia) was higher in tivozanib hydrochloride-treated subjects than in sorafenib-treated subjects. The incidence of off-target toxicities (palmar-plantar erythrodysesthesia, diarrhea, alopecia, and increased lipase) was lower in tivozanib hydrochloride-treated subjects than in sorafenib-treated subjects.

In this trial, 16 subjects experienced adverse events leading to death, and one of these AEs leading to death (hypertension) was considered probably related to study treatment. Three of the AEs were considered possibly related to study treatment (cerebrovascular, pulmonary embolism, post-procedural hemorrhage) and the remaining were unlikely related or unrelated to tivo.

| | Total Tivozanib | AV-951-09-301/902 Tivozanib |
|-----------------------------------|--------------------|--------------------------------|
| | (N=785) | (N=259) |
| Preferred Term | n (%) | n (%) |
| Any Adverse Event | 681 (86.8) | 235 (90.7) |
| Hypertension | 333 (42.4) | 113 (43.6) |
| Dysphonia | 176 (22.4) | 55 (21.2) |
| Fatigue | 173 (22.0) | 50 (19.3) |
| Diarrhea | 168 (21.4) | 59 (22.8) |
| Asthenia | 123 (15.7) | 40 (15.4) |
| Dyspnea | 111 (14.1) | 29 (11.2) |
| Back pain | 101 (12.9) | 35 (13.5) |
| Nausea | 99 (12.6) | 31 (12.0) |
| Decreased appetite | 89 (11.3) | 27 (10.4) |
| Cough | 85 (10.8) | 20 (7.7) |
| Palmar-plantar erythrodysesthesia | 82 (10.4) | 36 (13.9) |
| Weight decreased | 79 (10.1) | 47 (18.1) |

Pooled data from 4 core RCC monotherapy studies AV-951-07-201, AV-951-10-202, AV-951-09-902, and AV-951-09-301. From Tivozanib Hydrochloride Investigator Brochure, version 9.2, May 2012.

The incidence of hypertension and palmar-plantar erythrodysesthesia syndrome presented in this table include events of all grades. For the purposes of regulatory reporting, these events are considered expected at \leq CTCAE Grade 3. Higher grades are considered unexpected.

In other monotherapy studies AV-951-10-112, KRN951/03-B01, and AV-951-08-105, TEAEs were reported in 106 of the 109 subjects (47/50 [94.0%], 42/42 [100%], and 17/17 [100%], respectively). In general, the most frequently reported TEAEs in tivozanib hydrochloride-treated subjects across these 3 studies were hypertension (range of 41.2% to 59.5%), fatigue (26.0% to 76.5%), diarrhea (10.0% to 54.8%), nausea (16.0% to 52.9%), and headache (20.0% to 38.1%). The lowest incidence of TEAEs was observed in Study AV-951-10-112, in which subjects were administered tivozanib hydrochloride for only 3 weeks. Despite differences in dosing duration, and other factors such as underlying disease, dosing schedule, and the small number of subjects in each study, the TEAE patterns are generally consistent with those seen in the 4 core monotherapy studies.

When tivozanib hydrochloride is administered in combination with 1 or more approved antineoplastic agents, the expectedness determination should take into account the labeling of each specific marketed drug taken in combination based upon reference documents which will be included or referenced in the clinical study protocol. The labeled events should, in general, be

considered expected for at least one of the drugs in the combination. The contribution of tivozanib to the severity or frequency of the events is currently unknown.

2.1.2 Enzalutamide

Enzalutamide (MDV3100) is a small molecule antagonist of the androgen receptor (AR) that was originally selected based on its activity *in vitro* against prostate cancer cells that overexpressed androgen receptor⁴. In addition to binding tightly to AR, enzalutamide blocks nuclear translocation and DNA binding activity of AR, and furthermore has no known agonist activity against AR in contrast to previous generations of AR antagonists.

The rapid clinical development of enzalutamide is a testimony both to its clear efficacy against prostate cancer as well as its favorable tolerability profile. Clinical activity was observed at many dose levels, and the maximum tolerated dose for sustained treatment was 240 mg daily⁵. The dose chosen for subsequent trials was 160 mg daily. A randomized phase 3 trial of placebo versus enzalutamide in men with mCRPC was halted after an interim analysis demonstrated a

robust improvement in overall survival from 13.6 months to 18.4 months (P<0.0001)⁶. Treatment was well tolerated overall, and the most common reported side effects were fatigue and diarrhea. Early preclinical and clinical studies with enzalutamide raised a concern for an increased rate of seizures, and in the phase 3 trial, seizures were observed in 5 patients receiving enzalutamide (0.6%). Full efficacy and toxicity information is available in the package insert (http://www.astellas.us/docs/us/12A005-ENZ-WPI.pdf). Based on the results of the phase 3 trial, enzalutamide was approved by the US FDA for men with mCRPC previously treated with docetaxel chemotherapy.

Another phase 3 trial has studied the efficacy of enzalutamide in mCRPC patients who were chemotherapy naïve. This trial demonstrated a significant benefit in both primary endpoints, progression free and overall survival⁷. At 12 months, the rate of radiographic progression-free survival was 65% among enzalutamide-treated men, compared with only 14% among placebotreated men. All secondary endpoints similarly showed significant benefit to enzalutamide in this patient population.

2.2 Study Disease

Novel treatments for advanced prostate cancer are urgently needed. Despite the optimism engendered by a series of new approved therapies in the past three years, death due to prostate cancer will occur in an estimated 28,170 men in the United States in 2012, compared with 28,660 in 2008^{8,9}. Two classes of agents that have been studied in advanced prostate cancer are novel hormonal agents as discussed above, including the antiandrogen enzalutamide⁶ and the lyase inhibitor abiraterone⁷, and antiangiogenic agents such as bevacizumab¹⁰ and sunitinib¹¹.

2.3 Rationale

Among the most exciting recent results in prostate cancer research has been the demonstration that enzalutamide improves overall survival in metastatic, castration resistant prostate cancer (mCRPC)⁶. Enzalutamide is a novel pure antagonist of androgen receptor (AR) that functions by binding with high affinity to AR, preventing AR translocation to the nucleus, and ultimately inducing apoptosis of tumor cells. In the pivotal phase 3 trial, median survival in men previously treated with chemotherapy for mCRPC increased from 13.6 months to 18.4 months with the addition of enzalutamide⁶. There were also significant improvements in progression free survival (PFS) and other efficacy endpoints, with a median PFS of 8.3 months. Treatment with enzalutamide was well tolerated, in line with generally held and validated beliefs that effective hormonal agents offer substantial improvements in risk/benefit profiles compared with cytotoxic chemotherapy. A phase 3 trial with enzalutamide in chemotherapy-naïve patients with mCRPC has been completed, with results not yet available. Novel hormonal agents such as enz, abiraterone and others are unequivocally central to the current treatment paradigm in mCRPC.

The role of antiangiogenic therapy in prostate cancer is less certain, and at this time remains investigational. Two recent phase 3 trials, with bevacizumab and sunitinib respectively, failed to demonstrate an overall survival benefit for men with mCRPC receiving antiangiogenic therapy^{10,11}. However, each of these trials did show significant improvement in PFS. In the bevacizumab trial, men treated with docetaxel and prednisone (DP) had median PFS of 7.5

months, compared with 9.9 months in men treated with DP plus bevacizumab (P < 0.001). In the post-docetaxel sunitinib trial, men treated with prednisone alone had median PFS of 4.1 months, compared with 5.5 months in men treated with prednisone plus sunitinib (P < 0.001). It is not clear why the PFS benefits did not translate to overall survival benefits, but one plausible explanation may relate to tolerability. In the sunitinib trial, for example, more than 25% of men discontinued due to toxicity, likely blunting any signal for positive therapeutic impact. Additionally, both trials studied unselected populations of men with mCRPC, and conceivably there are particular subgroups of men who may benefit; predictive biomarkers of antiangiogenic response have not yet been validated in this patient population.

Tivozanib is a potent tyrosine kinase inhibitor (TKI) of VEGF receptors that has shown encouraging results in renal cell carcinoma³. Among the unique features of tivozanib are its marked selectivity for the VEGF receptors¹², as well as an outstanding tolerability profile that may be directly linked to this selectivity¹. The tolerability of tivozanib suggests that combination therapy with other classes of antineoplastic agents may be more feasible than previous attempts with other TKIs. However, it is likely that combining tivozanib with cytotoxic agents will still result in exaggerated adverse effects, as has been observed with bevacizumab and other VEGF pathway inhibitors. Therefore, it is of particular interest to attempt combination therapy with other targeted agents, and in prostate cancer, specifically with AR-targeted agents. Given the non-overlapping toxicity profile of tivozanib and enz, there is an opportunity to merge additive or potentially synergistic benefits by combining them in an appropriate patient population.

3. PARTICIPANT SELECTION

3.1 Eligibility Criteria

Participants must meet the following criteria on screening examination to be eligible to participate in the study:

- **3.1.1** Participants must have adenocarcinoma of the prostate that is metastatic or unresectable and for which standard curative options do not exist
- **3.1.2** Participants must have radiographic evidence of metastatic prostate cancer
- **3.1.3** Participants must have progressive disease despite ongoing androgen deprivation therapy (ADT) and castrate levels of testosterone, defined as castration resistant prostate cancer (CRPC)
- **3.1.4** Other than ongoing ADT, prior treatment with other hormonal agents such as antiandrogens or ketoconazole must have been stopped at least two weeks prior to enrollment

- **3.1.5** Participants may have received prior docetaxel-based chemotherapy for prostate cancer. Such chemotherapy must have been stopped at least three weeks prior to the first dosing in this study.
- 3.1.6 Male patients age ≥ 18 . Because no dosing or adverse event data are currently available on the use of enzalutamide or tivozanib in participants <18 years of age, children are excluded from this study.
- **3.1.7** Life expectancy of greater than 12 weeks
- **3.1.8** ECOG performance status ≤ 2
- **3.1.9** Participants must have normal organ and marrow function as defined below:
 - Absolute neutrophil count ≥ 1,500/mcL
 - Platelets $\geq 50,000/\text{mcL}$
 - total bilirubin $\leq 1.5 \times \text{ULN}$ (or $\leq 2.5 \times \text{ULN}$ for subjects with

asymptomatic Gilbert's syndrome)

- AST (SGOT)/ALT (SGPT) ≤ 2.5 X institutional upper limit of normal
- Creatinine $\leq 2x$ ULN
- Proteinuria < 3+ by urinalysis or urine dipstick
- **3.1.10** The effects of tivozanib and enzalutamide on the developing human fetus are unknown. For this reason, participating men must agree to use adequate contraception (hormonal or barrier method of birth control; abstinence) prior to study entry and for the duration of study participation.
- **3.1.11** Ability to understand and the willingness to sign a written informed consent document.

3.2 Exclusion Criteria

Participants who exhibit any of the following conditions at screening will not be eligible for admission into the study.

- **3.2.1** Prior treatment with enzalutamide, TOK-001, or ARN-509. Prior therapy with abiraterone or orteronel is permitted, but must have been stopped a minimum of two weeks prior to study entry. Prior and/or concurrent treatment with bone-targeted therapy such as bisphosphonates or denosumab is permitted.
- **3.2.2** Participants who have received more than two prior chemotherapy regimens for metastatic CRPC
- **3.2.3** Participants may not be receiving any other investigational anticancer agents

- **3.2.4** Participants with known brain metastases
- **3.2.5** History of allergic reactions attributed to compounds of similar chemical or biologic composition to tivozanib or enzalutamide
- **3.2.6** Radiotherapy or minor surgical procedure within 2 weeks, or major surgical procedure within 4 weeks prior to administration of first dose of study drug; inadequate recovery from prior surgical procedure
- **3.2.7** Any history of seizure or condition that may predispose to seizure
- **3.2.8** Significant cardiovascular disease, including
 - Uncontrolled hypertension: systolic blood pressure > 140 mmHg and/or diastolic blood pressure > 90 mmHg documented on 2 consecutive measurements taken at least 24 hours apart;
 - Myocardial infarction, severe angina, or unstable angina within 6 months prior to administration of first dose of study drug;
 - History of Class III or IV congestive heart failure, as defined by the New York Heart Association;
 - History of serious ventricular arrhythmia (ie, ventricular tachycardia or ventricular fibrillation):
 - Cardiac arrhythmias requiring anti-arrhythmic medications (except for atrial fibrillation that is well-controlled with anti-arrhythmic medication; and/or
 - Coronary or peripheral artery bypass graft within 6 months of screening
- **3.2.9** Non-healing wound, bone fracture or skin ulcer
- **3.2.10** Active peptic ulcer disease, inflammatory bowel disease, ulcerative colitis, or other gastrointestinal condition with increased risk of perforation; history of abdominal fistula, gastrointestinal perforation, or intra-abdominal abscess within 4 weeks prior to administration of first dose of study drug
- **3.2.11** Serious/active infection or infection requiring parenteral antibiotics
- **3.2.12** Significant thromboembolic or vascular disorders within 6 months prior to administration of first dose of study drug, including but not limited to:
- Deep vein thrombosis;
- Pulmonary embolism;
- Cerebrovascular accident (CVA) or transient ischemic attack (TIA)

- Peripheral arterial ischemia > Grade 2 (per National Cancer Institute [NCI] Common Terminology Criteria for Adverse Events [CTCAE] Version 4.0
 - **3.2.13** Corrected QT interval (QTc) of > 480 msec using Bazett's formula
 - **3.2.14** Currently active second primary malignancy, including hematologic malignancies, except for non-melanoma skin cancers, in situ cervical cancer, and ductal or lobular carcinoma in situ of the breast. Subjects are considered to have a currently active malignancy if they have completed anti-cancer therapy and have not been disease free for > 2 years.
 - **3.2.15** History of genetic or acquired immune suppression disease such as human immunodeficiency virus (HIV); subjects on immune suppressive therapy for organ transplant.
 - **3.2.16** Inability to swallow capsules, malabsorption syndrome or gastrointestinal disease that severely affects the absorption of study drugs, major resection of the stomach or small bowel, or gastric bypass procedure
 - **3.2.17** Significant bleeding disorders within 6 months prior to administration of first dose of study drug, including but not limited to:
- Hematemesis, hematochezia, melena or other gastrointestinal bleeding ≥ Grade 2 (per CTCAE Version 4.0);
- Hemoptysis or other pulmonary bleeding \geq Grade 2 (per CTCAE Version 4.0);
- Hematuria or other genitourinary bleeding \geq Grade 2 (per CTCAE Version 4.0).
 - **3.2.18** Psychiatric disorder or altered mental status precluding informed consent or protocol-related testing.

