4. REGISTRATION PROCEDURES

4.1 General Guidelines for DF/HCC and DF/PCC Institutions

Institutions will register eligible participants with the DF/HCC Quality Assurance Office for Clinical Trials (QACT) central registration system. Registration must occur prior to the initiation of therapy. Any participant not registered to the protocol before treatment begins will be considered ineligible and registration will be denied.

A member of the study team will confirm eligibility criteria and complete the protocol-specific eligibility checklist.

Following registration, participants may begin protocol treatment. Issues that would cause treatment delays should be discussed with the Principal Investigator. If a participant does not receive protocol therapy following registration, the participant's protocol status must be changed. Notify the QACT Registrar of participant status changes as soon as possible.

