5.1 Pre-treatment Criteria

All subjects must have the following within 21 days prior to start of protocol therapy:

- History and physical examination
- ECOG performance status
- Vital signs (including blood pressure, body temperature, heart rate and respiratory rate)
- Availability and review of prior medical records
- Concomitant medications
- Adverse event assessments
- Serum PSA
- Serum testosterone
- Complete blood count
- Serum chemistries
- Thyroid function test (TSH only)
- Coagulation studies
- Urinalysis (urine protein only)
- Electrocardiogram
- Chest x-ray

- Bone scan (repeat scans every 3 cycles up to Cycle 46 then repeat every 6 cycles)
- Abdomen/pelvic CT scan (repeat scans every 3 cycles up to Cycle 46 then repeat every 6 cycles)

Based on these studies, eligibility must be confirmed according to the guidelines in Section 3 above.

5.1.1 Day 1 of Cycle 1

The following data should be collected on Cycle 1 Day 1 (+/- 3 days):

- History and physical exam
- Concomitant medications
- Vital signs (including blood pressure, body temperature, heart rate and respiratory rate)
- ECOG performance status
- Complete blood count
- Serum chemistries
- Urinalysis (urine protein only)
- Adverse event assessments

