5.3.5. Other prohibited medications

Subjects should avoid agents known to be Cytochrome P450 (CYP3A4) inducers or inhibitors for the duration of study treatment. See Appendix B for a list of CYP3A4 inducers and inhibitors.

In addition, the following drugs should be avoided throughout the study period because they are known to lower seizure threshold or prolong the QT interval:

- Aminophylline/theophylline
- Atypical antipsychotics (e.g., clozapine, olanzapine, risperidone, ziprasidone)
- Bupropion
- Class IA and III antiarrhythmics (e.g., amiodarone, bretylium, disopyramide, ibutilide, procainamide, quinidine, sotalol)
- Dolasetron
- Droperidol
- Gatafloxacin/moxifloxacin
- Insulin
- Lithium
- Macrolide antibiotics (e.g., erythromycin, clarithromycin)
- Pethidine
- Phenothiazine antipsychotics (e.g., chlorpromazine, mesoridazine, thioridazine)
- Pimozide
- Tricyclic and tetracyclic antidepressants(e.g., amitriptyline, desipramine, doxepin, imipramine, maprotiline, mirtazapine)
- Venlafaxine

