Appendix B Cytochrome P450 (CYP3A4) Inducers/Inhibitors

| Cytochrome P450 (CYP3A4) Drug interaction table | | | |
|--|-----------------|--|--|
| INHIBITORS | INDUCERS | | |
| Amiodarone | Aprepitant | | |
| Cimetidine | Barbiturates | | |
| Clarithromycin | Carbamazepine | | |
| Diltiazem | Glucocorticoids | | |
| Erythromycin | Phenobarbital | | |
| Fluvoxamine | Phenytoin | | |
| Fruit Juices or products grapefruit, Seville orange, star fruit, and pomegranate | Rifabutin* | | |
| Indinavir | Rifampin* | | |
| Itraconazole | St. John's Wort | | |
| Ketoconazole* | Troglitazone | | |
| Mibefradil | | | |
| Nefazodone* | | | |
| Nelfinavir* | | | |
| Ritonavir* | | | |
| Troleandomycin | | | |
| Verapamil | | | |
| NOT azithromycin | | | |

[figure not shown]
^{*} Asterisk denotes strong inhibition / induction.

Strong inhibition implies that it can cause a > 5-fold increase in the plasma AUC values or > 80% decrease in clearance of sensitive CYP substrates. Moderate inhibitor implies that is can cause a > 2-fold increase in the plasma AUC values or 50-80% decrease in clearance of sensitive CYP substrates. Distinction is not always categorical as interaction can vary according to conditions.

This table is a guide and additional inducers/inhibitors may be identified. Please refer to the source of this table for any updated information: http://medicine.iupui.edu/clinpharm/ddis/

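### The atrial fibrillation exception in 3.2.8 lets a man qualify on a drug that Section 5.3.5 or Appendix B says he should avoid, and control without that drug need not be shown

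*Combined protocol and SAP*

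**What the plan says.** Section 3.2 is applied at screening: "Participants who exhibit any of the following conditions at screening will not be eligible for admission into the study". Under 3.2.8, one of the excluded cardiovascular conditions is "Cardiac arrhythmias requiring anti-arrhythmic medications", and the exception reads "except for atrial fibrillation that is well-controlled with anti-arrhythmic medication". It does not say which anti-arrhythmic drugs are acceptable.

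Section 5.3.5, whose title describes the drugs as prohibited, lists medications that "should be avoided throughout the study period because they are known to lower seizure threshold or prolong the QT interval". One entry is "Class IA and III antiarrhythmics (e.g., amiodarone, bretylium, disopyramide, ibutilide, procainamide, quinidine, sotalol". It makes no allowance for AF.

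Sections 5.3 and 5.3.5 separately say that CYP3A4 inducers and inhibitors should be avoided while on study treatment, and point to Appendix B. One row of that table reads "Amiodarone | Aprepitant", with the inhibitor on the left and the inducer on the right. Diltiazem and verapamil are also in the inhibitor column.

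On process, Section 5.1 says that "eligibility must be confirmed according to the guidelines in Section 3 above". Section 4.1 adds: "Following registration, participants may begin protocol treatment". Sections 3.2.8 and 5.3.5 do not refer to each other.

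**The concern.** The exception makes control on a drug the reason a man may enter. If that drug is on the avoid list, the treatment plan removes the basis on which he was admitted. The site then has two courses. It can leave him on an agent that the protocol says to avoid for its effect on QT or seizure threshold, or for its CYP3A4 interaction. Or it can stop the agent and treat a man whose AF control without it was never shown. The protocol does not say which course to take. What is at stake is the cardiac safety of a few men on a combination that, by the protocol's own account, has not been tested before, and consistency between sites in who is admitted.

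**Working it through.** The plan states no figure on this point, so there is none to reproduce. The check compares the rules for each kind of patient and then looks for any other step that closes the gap.

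**Inputs.** Section 3.2.8 (exception), Sections 5.3 and 5.3.5 (drugs to avoid), Appendix B (CYP3A4 list), Sections 5.1 to 5.1.3 and the Section 8 calendar (assessments), Section 4.1 (registration).

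**Step 1: the rules by drug controlling the AF.**

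| AF controlled on | Exception in 3.2.8 | Rules on drugs during the study |
|---|---|---|
| An agent on neither list | Met | No conflict |
| A Class IA/III agent, e.g. sotalol | Met | Should be avoided (5.3.5) |
| Amiodarone | Met | Should be avoided twice over (5.3.5; Appendix B) |
| Diltiazem or verapamil | Met, if the site counts it as anti-arrhythmic medication | Should be avoided (5.3, 5.3.5, Appendix B) |

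The last row rests on an assumption: the protocol does not say whether these two drugs count as anti-arrhythmic medication for 3.2.8.

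**Step 2: does another criterion limit the drug?** Section 3 has 11 inclusion and 18 exclusion criteria, 11 + 18 = 29. None limits the class of anti-arrhythmic used for AF. Section 5.3.5 names 7 Class IA/III agents as examples; 1 of the 7, amiodarone, is also in Appendix B. These are counts of text, not measures of risk.

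**Step 3: does a procedure test control without the drug?**

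- *Screening (5.1, within 21 days before therapy).* Concomitant medications are reviewed and an ECG is done, but eligibility is judged against Section 3, which has no class limit. The ECG shows the rhythm on whatever the man is taking that day.
- *Cycle 1 Day 1 (5.1.1).* History, examination, vital signs including heart rate, and concomitant medications are collected. A note in 5.1.2 lets the examination be skipped if done in the previous 7 days. A continuing listed drug, or a fast rate after a switch, could be noticed here. No rule says what follows, and no ECG is listed.
- *Later visits.* The calendar marks the ECG pre-study only, and the lists in 5.1.2 and 5.1.3 omit it.
- *Other exclusions.* QTc above 480 msec (3.2.13), seizure history or predisposition (3.2.7) and serious ventricular arrhythmia (3.2.8) reduce the baseline hazard. None tests whether AF stays controlled once the drug is withdrawn.

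**Result.** A man in rows two to four can satisfy every written entry criterion on a drug he should then avoid, and no written step requires control to be shown without it.

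**The case against.** The strongest reply is that the two sections do different jobs and a man must satisfy both: 3.2.8 asks whether the arrhythmia disqualifies him, and 5.3.5 governs what he takes on study. Switching a drug and rechecking the rhythm is ordinary care, Cycle 1 Day 1 gives an occasion for it, and Section 4.1 sends problems that would delay treatment to the Principal Investigator. This largely stands, and it rules out several stronger readings that a reader might infer.

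- *That the sections contradict each other.* They do not. A man on an unlisted agent meets both, and the avoid rules already apply at the first dose.
- *That nothing is checked between screening and treatment.* Medications, history, heart rate and, usually, examination are looked at again on Cycle 1 Day 1. What is missing is an AF-control criterion and a repeat ECG.
- *That the plan departs from its own practice of stating drug limits in both places.* It does so for hormonal agents (3.1.4 and 3.2.1 with 5.3.1), but not generally. The sipuleucel-T washout (5.3.2), full-dose warfarin (5.3.4) and other 5.3.5 drugs such as insulin, lithium and venlafaxine have no matching Section 3 criterion.
- *That starting on a listed drug is a clear violation.* Saying a drug should be avoided leaves room for clinical judgement, despite the section title.

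The eligibility checklist, which Section 4.2 makes the working screen, is not in the documents and may already deal with this.

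One thing survives. For insulin or lithium, eligibility does not depend on the drug. In 3.2.8 it does: control on medication is the condition of the exception, so withdrawing the drug removes the evidence for it. Ordinary care may fill the gap, but the criterion does not ask for it.

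**Conclusion.** The concern holds as a minor gap between eligibility and the rules on concomitant drugs. It reaches only men whose AF is controlled on a Class IA/III or Appendix B agent. Their number cannot be derived, because the documents give no frequency of AF or of anti-arrhythmic use; that it is small is a judgement. The conclusion assumes that the checklist follows Section 3 as written and that a site may read the exception as covering any agent used to control AF. A reader might infer that the trial's result is compromised; the documents do not support that. Nothing here enters the PFS definition, the one-sample test, the event target or the sample size.

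**What to change.** Reword the exception in 3.2.8 along these lines: *atrial fibrillation controlled without Class IA or III antiarrhythmics (Section 5.3.5) and without CYP3A4 inhibitors or inducers (Appendix B), with control on the current regimen documented at the pre-treatment evaluation, within 21 days before the start of therapy and including the screening ECG*. Carry the same wording into the eligibility checklist.

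Appendix B has to be named. A limit to Class IA/III alone would still admit a man controlled on diltiazem or verapamil, or let a site switch him to one of them. Tying control to the current regimen means that a man who is switched needs his ECG after the switch. The documents give no basis for a fixed washout, so that interval is left to clinical judgement.

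The cost is one phrase and one checklist line, submitted as a protocol amendment. The downside is that a few men are delayed or screened out. The documents do not state accrual status, and the change helps only men still to be registered.
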